#### **6.5 Study treatment interruptions**

Study drug may be interrupted at the Investigator's discretion for medical or surgical reasons.

Reasons for temporary study drug interruption may include a planned invasive procedure or surgery for which one would typically stop oral anticoagulation (see [Section 6.5.2](#)); clinical indication for a prohibited medication (see [Section 6.7.1](#)); a bleeding AE (see [Section 8.2](#)); or any other medical condition where the Investigator judges that it is in the best interests of the patient to temporarily interrupt study drug.

Since patients with AF are at underlying risk of stroke and systemic embolism, the duration of any study drug interruption should be kept to the minimum possible unless there is a contraindication to anticoagulation. Patients who have interrupted study drug should be re-evaluated regularly by the Investigator to determine the risks and benefits of resuming study drug.

For patients assigned to rivaroxaban, the eCRF page for study drug interruption should be completed for any temporary study treatment interruptions of 2 or more consecutive days and include the date/time of the last dose, the reason for the temporary interruption (e.g., procedures), and other required details.

For patients assigned to abelacimab, the eCRF for study drug interruption is required for any missed study treatment >45 days from the previous dose and include the date/time of the last dose, the reason for the temporary interruption (e.g., procedures), and other required details.

There is no limit on either the number of study drug temporary interruptions or the maximum length of a study drug temporary interruption. As long as the study has not completed, a patient who has interrupted study drug can resume study drug as soon as it is determined to be appropriate by the Investigator.

A patient who continues to be on study treatment interruption when the randomized period of the study has completed will be considered to have permanently discontinued study drug, will not be eligible for the extension and should complete a PSDD visit and a EoS visit approximately 30 days later (see [Section 6.6](#)).

Investigators are strongly encouraged to call the [REDACTED]

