### 7 Study Completion and Discontinuation

#### 7.1 Study completion and post-study treatment

The SSC will communicate to study sites when the study is ending. Sites will be instructed to schedule an end of treatment period (EoT) visit for randomized patients or end of extension treatment (EoE) visit for extension patients, as relevant:

- Patients assigned to one of the abelacimab treatment arms should have their EoT or EoE visit scheduled approximately 30 days after their last s.c. injection of study medication.
- Patients assigned to the rivaroxaban treatment arm should complete their EoT visit starting approximately two weeks after notification from the SSC. These patients should continue to take their assigned treatment up to the day prior to the EoT visit, at which time rivaroxaban supplies must be collected.

At the EoT visit or EoE (for patients completing the extension period), all study drug supplies must be collected from the patient and the Investigator must begin plans to transition the patient to SoC anticoagulation therapy according to the guidelines in [Table 7-1](#), unless the patient has a contraindication to anticoagulation therapy.

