### **10.1 Analysis sets**

- On-Treatment: will consist of all randomized patients who received at least one dose of study drug. Patients will be considered to be on-treatment if within 60 days of their last dose of study drug up to the EoT visit of the randomized treatment period.
- Intent-to-Treat (ITT): all patients randomized and dosed to be analyzed according to randomized treatment assignment. Events occurring from randomization through EoS of the randomized treatment period will be included in the analysis.
- Per Protocol: All randomized patients with a treatment compliance rate of at least 80% and do not have any major protocol violations as defined in the final SAP.
- On-Treatment Extension: will consist of all patients who received at least one dose of abelacimab in the extension period. Patients will be considered to be on-treatment if within 60 days of their last dose of study drug to the EoE visit of the extension period.

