### 3. Analysis Populations and Dates

#### 3.1. Analysis Dates

The analysis dates to be used are defined as:

- EoT date = Earliest of a) the last dose+60 days or b) the EoT visit or c) death date or d) withdraw consent date or e) EoS visit date
- EoS date = Earliest of a) EoS visit or b) death date or c) withdraw consent date or d) lost to follow-up date; if no EoS date available, then impute EoT visit date

In the event that there is an open-label extension period in which the patient enrolls, the following analysis dates to be used are defined as:

- EoT date = Earliest of a) the last dose+60 days or b) the EoT visit or c) death date
- EoS date = Earliest of a) the last dose+60 days or b) the EoT visit or c) death date
- EoE date = Earliest of a) the last dose+60 days or b) the EoE visit or c) death date
- EoS extension date = EoS visit; if no EOS visit date available, then impute EoE date

In accordance with ICH E3 and E9, the following analysis sets will be used for the analyses.

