### 2.1. Change in the EoT date and EoS date in the randomized phase of the study for patients enrolled in the extension in section 3.1 of the SAP

The analysis dates to be used are defined as:

- EoT date = Earliest of a) the last dose+60 days or b) the EoT visit **-1 day** or c) death date or d) withdraw consent date or e) EoS visit date
- EoS date = Earliest of a) EoS visit or b) death date or c) withdraw consent date or d) lost to follow-up date; if no EoS date available, then impute EoT visit date **-1 day**

**As per the protocol version 5.0, EoT visit and Extension Day 1 will occur on same day.** In the event that there is an open-label extension period in which the patient enrolls, the following analysis dates to be used are defined as:

- EoT date = **Earlier of a) the last dose+60 days or b) the EoT visit -1 day**
- EoS date = **the EoT visit -1 day**
- EoE date = Earliest of a) the last dose+60 days or b) the EoE visit or c) death date
- EoS extension date = EoS visit; if no EOS visit date available, then impute EoE date

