### 2.2. Change in the last dose dates in section 5.1.1 of the SAP

The date of the last dose of treatment for each patient will be taken from the eCRF page. For subjects receiving abelacimab, the last dose is latest Date of injection from the Study Drug SC Administration eCRF page (**before the extension day 1 for patients who enroll in the extension**).

For subjects receiving rivaroxaban, the last dose will come from the following sources, depending on the patient status:

- For those who permanently discontinue treatment, the last dose will be the permanent discontinuation date.
- For those who died but did not permanently discontinue treatment before death, the last dose will be the death date.
- For all other subjects who completed the treatment per the EoT visit page, the last dose will be the EoT visit date **-1 day**.
- If the last dose date is still missing, the last dose will be the last date pills were returned from the Study Drug PO Accountability page.

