**For subjects receiving rivaroxaban who enroll in the extension, the last dose will be the EoT visit date -1 day.**

### 2.3. Clarification on major bleeding type in section 6.6.1 of the SAP

The primary endpoint variable is defined as time to first event of composite of ISTH-defined major bleeding (**including non-intracranial events and the following cerebrovascular events: Hemorrhagic Stroke, Ischemic Stroke with Hemorrhagic Transformation, Other Intracranial/Intraspinal Hemorrhage**) or CRNM bleeding events occurring from randomization through EoT date.

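### Read literally, the SAP addendum ends the extension on-treatment window about 30 or 59 days after extension Day 1, because its last-dose definition for extension enrollees predates the extension

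*SAP*

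**What the plan says.** SAP 3.1 closes the extension on-treatment period with this rule: "EoE date = Earliest of a) the last dose+60 days or b) the EoE visit or c) death date". Addendum 2.1, written after database lock, edits the EoT and EoS lines next to it and carries the EoE line over unchanged. It also records that "EoT visit and Extension Day 1 will occur on same day". If there is no EoS visit, the extension EoS date is imputed from the EoE date.

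The last dose is defined only in SAP 5.1.1, among the general definitions. For abelacimab it was simply the latest recorded injection. For rivaroxaban patients who completed treatment it was the EoT visit date. Addendum 2.2 amends both. The abelacimab injection must now fall "before the extension day 1 for patients who enroll in the extension", and a closing sentence adds: "For subjects receiving rivaroxaban who enroll in the extension, the last dose will be the EoT visit date -1 day".

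Protocol 10.1 treats a patient who has had at least one extension dose of abelacimab as on-treatment if "within 60 days of their last dose of study drug to the EoE visit of the extension period". SAP 3.6 defines the On-Treatment Extension set by at least one extension dose and gives it no end date of its own.

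**The concern.** One term serves two dates that need different doses. The randomized-phase EoT date needs the last dose before the extension; the EoE date needs the last dose within it. Addendum 2.2 settles the term in favour of the first use, and its heading does not restrict the change to the randomized phase. Addendum 2.1 leaves the second use resting on the same term. As written, no injection given in the extension can be the last dose, so the 60 days run from a date before the extension began.

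For prior-abelacimab patients the conflict arises only from Addendum 2.1 and 2.2 read together. For prior-rivaroxaban completers it was already in SAP 5.1.1, which placed their last dose at the EoT visit and had no rule for later abelacimab injections.

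At stake are the extension on-treatment summaries. Protocol 10.5.1.2 reports adverse events and exposure-adjusted rates on the On-Treatment Extension set, and Protocol 3.5 gives long-term data on abelacimab as a reason for the extension. A window counted from a pre-extension dose would also close at different times according to the arm a patient came from.

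**Working it through.** The plan gives no figure of its own here, so there is nothing to reproduce; the check is date arithmetic.

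**Inputs**
- Day 0 = EoT visit = extension Day 1 (Addendum 2.1).
- Close of window by the dose limb = last-dose offset + 60 days (SAP 3.1, Addendum 2.1).
- Prior abelacimab: Protocol 7.1 says these patients "should have their EoT or EoE visit scheduled approximately 30 days after their last s.c. injection of study medication", so the last-dose offset is about -30.
- Prior rivaroxaban: last dose = EoT visit - 1 day (Addendum 2.2), so the offset is -1.
- For a long gap between injections I use 45 days, from Protocol 6.5, where "the eCRF for study drug interruption is required for any missed study treatment >45 days from the previous dose".

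**As written**

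| Arm before extension | Last-dose offset | Offset + 60 = days after extension Day 1 |
|---|---|---|
| Abelacimab, 30-day gap | -30 | 30 |
| Abelacimab, 25-day gap | -25 | 35 |
| Abelacimab, 35-day gap | -35 | 25 |
| Abelacimab, 45-day gap | -45 | 15 |
| Rivaroxaban, Addendum 2.2 | -1 | 59 |
| Rivaroxaban completer, SAP 5.1.1 before the addendum | 0 | 60 |

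The 25- and 35-day gaps are assumed values around the protocol's approximate 30. These are latest closing dates: an EoE visit or death before then closes the window sooner.

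**Share of follow-up inside the window.** The extension length is not visible, so the lengths below are assumptions. Share = closing day / length.

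| Assumed length | Prior abelacimab | Prior rivaroxaban |
|---|---|---|
| 180 days | 30/180 = 17% | 59/180 = 33% |
| 365 days | 30/365 = 8% | 59/365 = 16% |
| 730 days | 30/730 = 4% | 59/730 = 8% |

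**With the last extension dose instead.** Protocol 7.1 places the EoE visit about 30 days after the last injection. For an extension of length L the last injection is at about L - 30, and the dose limb gives L - 30 + 60 = L + 30, which is later than the EoE visit at L. The EoE date is then the EoE visit for completers, and the 60-day limit binds only for patients who stop abelacimab early. This matches Protocol 10.1 read in its natural sense.

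**The case against.** The strongest reply is that the extension is analysed elsewhere. SAP 2.1 announces a separate analysis plan for extension data; it is not among the documents and may define its own last dose. Within this SAP, the EoE date appears in the definitions but in no analysis visible in Section 6, and treatment-emergent adverse events in SAP 6.7.3 run to the end-of-study visit. Addendum 2.1 is headed as a change to the randomized phase, and the wording added in 2.2 is evidently meant to keep extension injections out of the randomized-phase last dose. Membership of the extension set requires an extension dose, so a careful programmer would probably count from the last one.

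Most of this stands, and it limits the point. A reader might infer that almost all the long-term extension data will be excluded from reporting. The documents do not support that: all the data are still collected, the governing extension SAP is not visible, and the proportion depends on an unknown extension length. A reader might also infer a direct contradiction with Protocol 10.1. The two formulas have the same form; they part only once Addendum 2.2 supplies the dose.

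What the reply does not remove is that SAP 5.1.1 is the only definition of last dose in these documents, that Addendum 2.2 amends it without restricting it to the randomized phase, and that Addendum 2.1 still states an EoE rule built on it. That is a stated rule giving a wrong date, which is more than a missing detail.

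**Conclusion.** The EoE rule is wrong as written and should be corrected. Applied literally, it closes the extension on-treatment window no later than about 30 days after extension Day 1 for prior-abelacimab patients (15 to 35 days for gaps of 45 down to 25 days) and 59 days for prior-rivaroxaban patients. The 59 follows exactly from the text; the 30 is approximate because the visit spacing in Protocol 7.1 is approximate. The percentages above are illustrations only.

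The reach is narrow: extension on-treatment summaries, and the extension EoS date where there is no EoS visit. The randomized-period primary and secondary analyses use the EoT and EoS dates and do not change. This looks like a drafting gap rather than an intended rule. Whether any result is affected depends on the extension SAP and on how the date was programmed.

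**What to change.** In Addendum 2.1 and 2.2:

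1. State that the pre-extension last dose applies only to the randomized phase, where it sets the EoT date, and not to the EoE date.
2. Define the last extension dose as the latest abelacimab injection on or after extension Day 1, whichever arm the patient came from.
3. Define the EoE date as the earliest of last extension dose + 60 days, the EoE visit, or death.

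Alternatively, delete the EoE line and refer to the extension SAP, provided that plan uses this definition. If extension datasets already exist, check which dose the derivation used and document it.

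The cost is one definition and one derived date. No new data are needed, and no randomized-period result has to be rerun.

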**Table 7-1 End of Study Transition Guidelines**

Transitioning to	Instructions
Direct oral anticoagulant (DOAC)	Patients should initiate oral DOAC on the same day of the EoT/EoE visit.
Vitamin K antagonist (VKA)	Patients should be given a supply of VKA and instructed to begin therapy 3 to 5 days before the EoT visit. At the EoT visit, measure PT/INR and repeat as frequently as necessary until the PT/INR is therapeutic. Sites may collect repeat INR samples using point of care devices or send for local analysis, in which case results will remain as part of source documentation only.

The EoS visit (in-person or telephone/video-call) will take place approximately 4-weeks after the EoT/EoE visit. This visit will assess patients for a general health and safety check prior to concluding their participation in the study.

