## 2. Protocol Details

### 2.1. Overall Study Design

This is a Phase 2b, event-driven, randomized, active-controlled, blinded endpoint, parallel-group study to evaluate the effect of two blinded doses of abelacimab relative to open-label rivaroxaban on the rate of major or clinically relevant non-major (CRNM) bleeding events in patients with atrial fibrillation (AF) who are at moderate-to-high risk of ischemic stroke.

Randomization into treatment groups will be stratified by the use of concomitant antiplatelet use at baseline (yes/no) and renal function (creatinine clearance [CrCl]  $\leq$ 50 ml/min or CrCl  $>$ 50 ml/min).

Eligible patients will be randomized into one of the following treatment groups:

- Treatment group 1: abelacimab 90 mg subcutaneous (s.c.) monthly
- Treatment group 2: abelacimab 150 mg s.c. monthly
- Treatment group 3: rivaroxaban 20 mg orally (p.o.) once per day with the evening meal [Note: Patients with a CrCl  $\leq$ 50 ml/min by the Cockcroft-Gault equation will receive the 15 mg p.o. daily dose of rivaroxaban]

The study is comprised of up to 4 periods: 1) screening (up to 4 weeks), 2) study drug treatment period through the end of treatment period (EoT) visit, 3) an optional extension period beginning at the EoT visit for qualifying patients to receive open-label abelacimab treatment (OLE period) if the study is discontinued early, and 4) transition period to appropriate standard of care (SoC) antithrombotic therapy per the discretion of the investigator through the End of Study (EoS) visit.

When the prespecified number of adjudicated clinical endpoint events for the final analysis have been reached, or if the study is to be stopped for any other reason, sites will be notified by the Sponsor's Clinical Study Team to schedule each patient for their EoT visit. As part of the EoT visit, the Investigator will make arrangements to transition the patient to the extension treatment period, or to end the study by transitioning the patient to a standard-of-care anticoagulation therapy following the guidelines in Section 7.1 of the protocol.

[figure not shown]
A separate statistical analysis plan will be created for the analysis of data in the study extension treatment period.

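### The extension's end-of-study date in SAP 3.1 has no death, withdrawal or lost-to-follow-up term, so a death between the EoE and EoS visits would fall outside any analysis window that uses it

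*SAP*

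**What the plan says.** SAP 3.1 sets the dates that bound each follow-up period. For the end of the extension study period it gives "EoS extension date = EoS visit; if no EOS visit date available, then impute EoE date". The fallback is defined one line above: "EoE date = Earliest of a) the last dose+60 days or b) the EoE visit or c) death date".

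For patients who do not enter the extension, the same section gives "EoS date = Earliest of a) EoS visit or b) death date or c) withdraw consent date or d) lost to follow-up date", with the EoT visit date imputed if none is available. The main EoT date there also includes withdrawal of consent; the EoE date does not.

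Addendum 2.1, written after database lock, changes the randomized-phase EoT and EoS lines and repeats the two extension lines unaltered.

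The visit spacing comes from Protocol 7.1. Abelacimab patients "should have their EoT or EoE visit scheduled approximately 30 days after their last s.c. injection of study medication", and the EoS visit "will take place approximately 4-weeks after the EoT/EoE visit". Protocol 3.1.4 makes four weeks a minimum, counted from EoE or from the start of standard-of-care anticoagulation, whichever is longer.

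SAP 2.1 states: "A separate statistical analysis plan will be created for the analysis of data in the study extension treatment period". That plan is not among the documents.

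**The concern.** The extension rule makes the length of follow-up depend on the outcome. A patient who is alive and attends the EoS visit is followed to that visit. A patient who dies before it has no EoS visit, so the end of follow-up moves back to EoE and the death lies after it. The death term in the EoE date does not help, because an earliest-of rule cannot select a death that comes after an EoE visit that has already taken place.

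The interval affected is the transition from open-label abelacimab to another anticoagulant. Protocol 3.5 gives collection of long-term data as a purpose of the extension, and Protocol 3.1.6 keeps bleeding, cerebrovascular and systemic embolic events under central review during it. In any summary run to this date, a fatal event in the interval would be left out while survivors contributed their event-free time and their non-fatal events.

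The missing withdrawal term in the EoE date works the other way. A patient who withdraws without an EoE visit stays in the window until 60 days after the last dose, although Protocol 7.3 defines withdrawal as the end of all study contact.

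**Working it through.** There is no planned figure to reproduce. The check applies the date rules literally.

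**Inputs.** Last injection is day 0. The EoE visit is on day 30 (Protocol 7.1). The EoS visit is due on day 30 + 28 = 58 (Protocol 7.1). The death days are assumptions.

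**Rules.**
- EoE date = min(last dose + 60, EoE visit, death).
- EoS extension date now = EoS visit if there is one, otherwise the EoE date.
- EoS extension date as proposed = earliest of EoS visit, death, withdrawal or loss to follow-up, otherwise the EoE date.

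| Patient | EoE date | EoS extension date now | Position of death | As proposed |
|---|---|---|---|---|
| Survivor, EoS visit day 58 | 30 | 58 | none | 58 |
| Dies day 20, before EoE | 20 | 20 | inside | 20 |
| EoE visit day 30, dies day 31 | 30 | 30 | 1 day outside | 31 |
| EoE visit day 30, dies day 44 | 30 | 30 | 14 days outside | 44 |
| EoE visit day 30, dies day 57 | 30 | 30 | 27 days outside | 57 |
| Early stop, no EoE or EoS visit, dies day 75 | 60 | 60 | 15 days outside | 75 |

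Deaths before both the EoE visit and last dose + 60 days are captured through the fallback. The gap is confined to later deaths with no EoS visit.

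**Withdrawal.** Suppose a patient withdraws on day 10 with no EoE or EoS visit. The EoE date is day 60, so 60 − 10 = 50 days without contact are counted as follow-up. With a withdrawal term the date is day 10.

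**Illustrative size.** Expected deaths between EoE and EoS = N × (28 / 365.25) × annual mortality. Neither N nor mortality is in the documents. The 1,287 patients randomized (Protocol 1.2.2) are a ceiling for N.

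| Assumed N | Patient-years in the gap | Deaths at 3% | Deaths at 6% |
|---|---|---|---|
| 500 | 38.3 | 1.1 | 2.3 |
| 1,000 | 76.7 | 2.3 | 4.6 |
| 1,287 | 98.7 | 3.0 | 5.9 |

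**Use of the date.** SAP 6.6.1 runs the primary analysis to the EoT date, SAP 6.6.3 analyzes the secondary endpoints by the same procedures, and the ITT sensitivity analysis in SAP 6.6.2 runs to the randomized-phase EoS date. SAP 3.6 defines the extension analysis set without a follow-up window. No analysis in the visible text cites the EoS extension date.

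**The case against.** The strongest reply is that the date has no shown consequence. No visible analysis uses it, and the extension is assigned to a separate plan that may define its window differently. The extension window that Protocol 10.1 does define, on-treatment up to 60 days after the last dose or the EoE visit, closes by EoE for survivors and for those who die alike. Protocol 10.5.1.2 summarizes extension adverse events in that set. On that window there is no selection on outcome. This stands, and it limits the point to analyses that run to the EoS extension date.

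A reader might infer that these deaths are lost. The documents do not support that. Protocol 8.4.2 requires SAE reporting until 30 days after the last planned assessment, and Protocol 3.1.7 continues DMC oversight through the extension. The rule sets a date; it does not delete a recorded death.

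The day-75 case is also weaker than it looks. For the EoE date, leaving out a death more than 60 days after the last dose is the intended on-treatment cut, and the randomized-phase EoT date has the same cut. In addition, an off-drug patient may already have had an EoS visit about 30 days after the permanent-discontinuation visit (Protocol 6.6). An earliest-of rule would then also close before a later death.

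Finally, Addendum 2.1 is titled as a change to randomized-phase dates, so its repetition of the extension lines is weak evidence that they were reconsidered. It does mean that they were left uncorrected.

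None of this defends the wording. The SAP lists the EoS visit and the death date as separate terms in the comparable rule, so the death cannot be assumed to stand in for the visit. As the supplied documents stand, this is the only definition of the extension's end-of-study date.

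**Conclusion.** The definition is defective and should be corrected. Any extension analysis that runs to the EoS extension date would close a patient who dies between the EoE and EoS visits at EoE, with the death outside the window, while survivors are followed to EoS. That follows directly from the text and the protocol's visit spacing.

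The consequence is conditional. A reader might conclude that mortality, fatal bleeding or stroke after open-label abelacimab is understated. The documents do not show that, because they contain no analysis using this date and the extension SAP is not supplied. The randomized primary and secondary results are unaffected. The 2.3 to 4.6 deaths at 1,000 patients rest on an assumed extension size and an assumed mortality. They indicate scale only and do not estimate bias in a planned result. Protocol 3.1.4 allows a gap longer than 28 days, which would raise the count in proportion.

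**What to change.** In SAP 3.1 and Addendum 2.1, define the EoS extension date as the earliest of the EoS visit, the death date, the withdrawal-of-consent date and the lost-to-follow-up date, with the EoE date imputed if none of these is available. This mirrors the rule the SAP already has for patients who do not enter the extension. Add the withdrawal-of-consent date to the EoE date, to match the main EoT rule. Carry both definitions into the extension SAP, and state there which analyses stop at EoE and which run to EoS.

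The cost is two lines of wording and a small programming change. The same kinds of date already feed the randomized-phase rules, so no new data are needed. Dates do not change for survivors who attend EoS or for patients who die before EoE. Event counts in any extension summary that runs to EoS may rise slightly.
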